Purpose: The first part of our study will evaluate whether minimal support through weekly automated messaging helps people with MS adhere to a calorie restricted diet. It will also evaluate the effect of weight loss, particularly abdominal obesity, on fatigue and health-related quality of life in patients with MS. The second program will evaluate if shortening the period during the day in which people consume their typical food amounts leads to improvements in patient-reported outcomes or markers of metabolism.

Hypotheses: Intermittent reminders about the importance of adhering to a dietary intervention combined with use of a calorie-tracking smartphone application will improve adherence over use of the application alone. Weight loss, especially decreased abdominal obesity, will improve fatigue and quality of life in patients with MS. Even in people who are not reducing their calorie intake, consuming those calories within a shorter time period within each 24 hours will improve metabolic markers and patient-reported outcomes.

2. Objectives (include all primary and secondary objectives)

Primary Objective. To evaluate if automated messaging support helps people with MS adhere to calorie restriction diet. We predict that intermittent reminders about the importance of adhering to a dietary intervention combined with use of a calorie-tracking smartphone application that is intermittently shared with the study team, will lead to better adherence than use of the application alone in overweight and obese people with MS.

Secondary Objectives. A) To assess the effect of weight loss, particularly reduced abdominal obesity, on fatigue, health-related quality of life, and self-esteem in overweight and obese people with MS. Based on the current literature, we hypothesize that weight loss will improve these aspects of patient well-being.

B) To assess if shortening the time period in which typical calories are consumed during the day improves markers of metabolism, fatigue, or health-related quality of life in people with MS. We hypothesize that consolidating calories consumed into a shorter period of the day leads to improvements in metabolism and patient-reported outcomes.

1. Background

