Dietary modification represents an intriguing potential MS intervention. **One aspect of diet that shows promise involves calorie intake.** Calorie restriction or fasting prior to the induction of experimental autoimmune encephalomyelitis (EAE), a mouse model of MS, is associated with a less aggressive course.^{11,12} There may be several mechanisms by which this occurs. **Calorie restriction and fasting are associated with reductions in pro-inflammatory cytokines** and other inflammatory markers in EAE mice^{11,12} and in humans who are healthy, obese, or have asthma, similar reductions have been observed.¹³⁻¹⁶ Ceramides are elevated in MS patients and pathogenic in vitro;¹⁷ calorie restriction reduces their levels in humans without MS.¹⁵ Calorie restriction also reduces markers of oxidative stress,¹⁵ and thus may reduce mitochondrial dysfunction. Beyond its direct biological effects, optimization of weight may lead to improvements in MS-related symptoms such as fatigue as well as in health-related quality of life, as overweight MS patients have been shown to have lower self-rated measures of well-being than controls.^{18,19} As such, **there is a strong rationale for evaluating the benefits of calorie restriction in MS.** The timing of calorie intake may also be critical, suggesting a possible rationale for consolidating the time period in which typical calories are consumed.

2. Study Procedures

a. Study design, including the sequence and timing of study procedures

Calorie restriction study:

Overview: We will conduct a pragmatic pilot study in which 80 patients with MS who are undergoing monthly infusions with natalizumab and who are overweight or obese are offered enrollment in this trial. Participants who consent will undergo a basic evaluation of total energy expenditure. At baseline, participants will participate in a short training about intermittent versus continuous calorie restriction and will choose the dietary intervention they'd prefer to use. The LoseIt! Application will be installed on the participants' smartphones, and they will receive training in utilizing the application. Baseline assessments of health-related quality of life (HRQoL), fatigue, self-esteem and physical activity will be conducted. Serum and plasma will be collected for future studies.

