- Health-related quality of life, (Functional Assessment in MS [FAMS]), fatigue (PROMIS fatigue), Pittsburgh Sleep Quality Index (PSQI), timing of sleep (Morningness-Eveningness Questionnaire [MEQ]), self-esteem (Rosenberg Self-Esteem Scale) and physical activity (International Physical Activity Questionnaire) assessments
- Blood for future research collected (30 ml)
- Coaching about the two diet options
- Installation of LoseIt! application on smartphone
- Determination of baseline energy requirement (*see below*)
- Randomization group assigned (participant blinded)
- Stool sample kit collection

At follow-up visits (months 3 and 6), the following will be done:

- Vital signs and waist circumference
- Patient-Determined Disease Steps (month 6 only)
- Health-related quality of life (Functional Assessment in MS [FAMS]), fatigue (PROMIS fatigue), Pittsburgh Sleep Quality Index (PSQI), timing of sleep (Morningness-Eveningness Questionnaire [MEQ]), self-esteem (Rosenberg Self-Esteem Scale) and physical activity (International Physical Activity Questionnaire) assessments
- Blood for future research (30 ml/visit)
- Stool sample kit distribution (at month 3) and collection (at month 6)
- Collection of LoseIt! application data (calorie counts) since prior visit

Determination of Baseline Energy Requirement and Diet Details: The baseline energy requirement (total energy expenditure) of each participant will be determined prior to randomization. This measurement is defined as the number of calories needed to maintain the current body weight. Total energy expenditure will be assessed using validated equations from University of Arizona Calorie Need Estimates, which include an individual's estimated resting

Date: 7/20/16

Principal Investigator: [name], MCR

Application Number: IRB00095554

energy expenditure (based on current weight, height and age) and physical activity (based on the International Physical Activity Questionnaire short form).

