For the primary objective, the impact of increased patient engagement via the smartphone on weight loss (pounds lost, change in body mass index, and change in waist circumference) as well as on the percentage adherence to the recommended calorie intake (as assessed by LoseIt! logs) will be evaluated in t-tests. If there are baseline imbalances in potentially meaningful covariates despite randomization, multivariate approaches accounting for imbalanced covariates will be employed.

For the secondary objective, the primary analysis will evaluate the association of weight loss (change in body mass index as well as change in waist circumference) with changes in health-related quality of life, sleep and fatigue using multivariate linear regression adjusted for age, sex, race, change in physical activity and baseline disability. Whether group assignment (extra smartphone engagement or standard of care) influences this relationship will also be evaluated.

The rationale for measuring change in waist circumference as the primary outcome is that waist circumference, rather than body mass index, is considered a better measure of the risk of metabolic syndrome.²⁰ However, for comparability with previously-published studies and in order to further evaluate the relationship between waist circumference with body mass index, both measures will be obtained.

Calorie Timing:

Metabolomics will be conducted on samples from the participants to evaluate the impact of restricting the hours in which foods are consumed. Primary analyses will be intent-to treat; secondary analyses will investigate with the actual time of day metrics, as assessed by time stamps of smartphone photos, are predictive of changes in metabolism. Secondary outcomes will be assessed as above.

d. Early stopping rules.

Participants who become pregnant, experience weight loss with BMI < 20 kg/m², or who develop another issue that, in the estimation of the investigator, puts them at risk of ongoing participation, the participant will be asked to cease following the diet but will be followed to the completion of the study.

6. Risks

a. Medical risks, listing all procedures, their major and minor risks and expected frequency.

- Calorie-restriction diet
 - The risks associated with the diets are not known
 - Previous studies of similar diets in humans have not shown any serious risks.
 -

-
- Calorie timing diet
 - Participants may be hungrier in the time in which foods are not being consumed

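### The only model for Secondary Objective A adjusts for concurrent change in physical activity and omits baseline values already collected, so its single estimate may understate or distort the weight-loss association

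*Combined protocol and SAP*

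**What the plan says.** Secondary Objective A in the Objectives section is causal in wording: "To assess the effect of weight loss, particularly reduced abdominal obesity, on fatigue" and other patient-reported outcomes.

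The analysis is in section 5c, under Calorie Restriction. It takes change in BMI and change in waist as the exposures and is described there as an association, "with changes in health-related quality of life, sleep and fatigue using multivariate linear regression". The covariate set is short; the model is to be "adjusted for age, sex, race, change in physical activity and baseline disability". The plan then turns to the arms: "Whether group assignment (extra smartphone engagement or standard of care) influences this relationship will also be evaluated". The plan gives no reason for including change in physical activity, and no version of the model without it. The baseline value of the outcome score, baseline BMI or waist, and baseline activity are not in the covariate list.

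These values will be in hand. The overview in section 2a states: "Baseline assessments of health-related quality of life (HRQoL), fatigue, self-esteem and physical activity will be conducted". The baseline list and the month 3 and 6 list both include vital signs, waist, the quality-of-life, fatigue and sleep questionnaires, and "physical activity (International Physical Activity Questionnaire) assessments".

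**The concern.** Weight loss is not randomised, so the choice of covariates decides what the slope means. Two choices matter here.

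- **Activity change.** Becoming more active may cause both weight loss and less fatigue (confounder). Losing weight may make people more active, and activity may then reduce fatigue (mediator). Both weight loss and lower fatigue may raise activity (collider). All three quantities are recorded at the same visits, so the data cannot order them in time. A single adjusted estimate answers a different question in each case.
- **Baseline values.** A change score without its baseline is noisier than it need be. If people with worse baseline fatigue or quality of life are more or less likely to lose weight, regression to the mean can enter the slope. Baseline disability is only a partial stand-in for the baseline score.

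Arm may also act on both sides. According to the adherence section, the messages promote weight loss and, where possible, describe how it may benefit MS. They could therefore shift questionnaire answers directly.

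At stake is whether the reported coefficient can be read as bearing on the stated objective, and whether the model is fixed before results are seen.

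**Working it through.** The plan gives no figure to reproduce. It states 80 participants randomised 1:1, but no standard deviation, effect size or baseline-to-follow-up correlation for this objective. Every path and correlation below is an assumption. For scale, a standardised slope at n = 80 has a standard error of about 1/√80 = 0.11.

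**1. Role of activity change.** Take a direct effect of weight loss on the outcome of 0.30, an activity–outcome path of 0.30, and a path g = 0.2, 0.3 or 0.4 between weight loss and activity. Outcomes are oriented so that higher is better.

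- Confounder or mediator, activity left out: 0.30 + 0.30g.
- Confounder or mediator, activity included: 0.30.
- Collider, activity included: 0.30 − [0.30/(1 + 0.30²)] × (g + 0.30 × 0.30) = 0.30 − 0.275 × (g + 0.09).

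| Role | Target | Without activity change | With activity change |
|---|---|---|---|
| Confounder | 0.30 | 0.36, 0.39, 0.42 | 0.30 |
| Mediator (total) | 0.36, 0.39, 0.42 | 0.36, 0.39, 0.42 | 0.30 |
| Collider | 0.30 | 0.30 | 0.22, 0.19, 0.165 |

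Large-sample simulation agrees with these values to within 0.002.

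A true zero can also be moved. With standardised activity and collider paths a and b, the spurious slope has size ab/(1 − a²). This is 0.09/0.91 = 0.10 for a = b = 0.3 and 0.25/0.75 = 0.33 for a = b = 0.5, about one to three standard errors. If weight loss raises activity and fatigue lowers it, the shift works against the hypothesised benefit.

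**2. Precision lost by omitting the baseline score.** Let r be the baseline-to-follow-up correlation, with equal variances and weight loss unrelated to the baseline score. Residual variance is 2(1 − r) for the change score and 1 − r² with baseline included, so the ratio is 2/(1 + r).

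| r | Variance ratio | SE ratio | 80 patients carry the information of |
|---|---|---|---|
| 0.3 | 1.54 | 1.24 | 52 |
| 0.5 | 1.33 | 1.15 | 60 |
| 0.7 | 1.18 | 1.08 | 68 |
| 0.9 | 1.05 | 1.03 | 76 |

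The gain shrinks if weight loss is correlated with the baseline score. At a correlation ρ = 0.3 the two variances become 2(1 − r) − (1 − r)²ρ² and (1 − r²)/(1 − ρ²). For r = 0.5 these are 0.978 and 0.824 (SE ratio 1.09). For r = 0.7 they are 0.592 and 0.560 (SE ratio 1.03).

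**3. Bias from the handling of baseline, when the true effect is zero.** Let ρ be the correlation of weight loss with the observed baseline score.

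- If weight loss depends on the observed score, the change-score slope is (r − 1)ρ and the baseline-adjusted slope is zero. For ρ of 0.1 to 0.3, the size is 0.05 to 0.15 at r = 0.5 and 0.03 to 0.09 at r = 0.7.
- If weight loss depends on a stable underlying level that the questionnaire measures with error, the change-score slope is zero and the baseline-adjusted slope is ρ(1 − r)/(1 − ρ²). This runs from 0.1 × 0.3/0.99 = 0.03 to 0.3 × 0.5/0.91 = 0.16.
- If ρ = 0, neither form is biased.

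The two possible errors are of similar size, and the documents do not say which case applies.

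**The case against.** The rule against post-baseline covariates protects a randomised comparison. Here the exposure is itself a post-baseline, non-randomised change, so the rule does not carry over. Activity change is a credible confounder, and in that case the plan's adjustment is the correct one. This stands: a reader might infer that adjusting for activity change makes the estimate wrong, and the documents do not support that. They also give no basis for ranking the unadjusted model above the adjusted one.

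The change-score form is also defensible. A reader might infer that omitting the baseline score is simply an error with no trade-off, but the third calculation shows that adding it can create a bias as large as the one it removes. This stands too, and it is why both forms should be shown.

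A reader might also infer that arm is ignored. It is not: section 5c will examine whether group assignment influences the relationship, which would ordinarily bring arm into a model. What remains is that arm is not in the stated adjustment set.

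Finally, section 5c speaks of an association, and this is a secondary analysis in a pilot. That limits the stakes. It does not remove the mismatch with the objective's causal wording, or supply a reason for the covariate choice.

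**Conclusion.** The point holds as a weakness of specification, not as a demonstrated bias. The only model for Secondary Objective A yields one activity-adjusted slope. That slope may equal, understate or distort the total association, depending on a causal role that the documents leave open. In the illustrative cases the gap runs from nothing (confounder) through 0.06 to 0.12 (mediator) to 0.08 to 0.135 (collider with a true 0.30), and a true zero can move by 0.10 to 0.33 in the collider case.

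Omitting the baseline score costs about 8% to 15% in standard error for r of 0.7 to 0.5, or about 3% to 9% if weight loss and the baseline score correlate at 0.3. It may also bias the slope by up to 0.15 in the range tried, but only if weight loss is related to the observed baseline score.

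All of this rests on assumed correlations and paths. The randomised comparison of the arms on waist circumference does not use this model and is unaffected. The change is worth making because the data are already collected and a prespecified pair of models prevents choosing after the results are known.

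**What to change.** In section 5c, replace the single model for Secondary Objective A with the following:

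- **Two co-reported models**, one with and one without change in physical activity, neither ranked as correct. State what each estimates (an activity-adjusted and a total association) and why activity change is considered.
- **In both models**, keep age, sex, race and baseline disability. Add the baseline value of the same questionnaire score, baseline BMI or waist (matching the exposure), baseline physical activity, and randomised arm as a main effect. The planned look at whether arm modifies the relationship can follow.
- **A sensitivity analysis** using the planned change-score form without the baseline score, because weight loss is not randomised and neither form is always unbiased.
- **Wording** that reports the result as an association, with the objective's language brought into line.

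The cost is one paragraph of text, four further terms (a few degrees of freedom at n = 80) and a little more analysis and reporting. No new data are needed.

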Overview: We will conduct a pragmatic pilot study in which 40 patients with MS who are undergoing monthly infusions with natalizumab and who are either not overweight or obese, or who do meet criteria for the calorie restriction study but refuse to participate, are offered enrollment in this trial. At baseline, participants will be assessed to ensure they know how to take pictures with and save them on their smartphones. Baseline assessments of health-related quality of life (HRQoL), fatigue, self-esteem and physical activity will be conducted.

Participants will then be randomized to one of two groups: 1) to not changing their current dietary patterns at all, or 2) to consuming their total daily calories within a period of 12:00 PM and 8:00 PM. Serum and plasma will be collected for future studies.

Enrollment and Randomization: In order to maximize enrollment within the period of support, people with MS who receive monthly natalizumab infusions and meet other criteria (see #3 inclusion/exclusion criteria) will be offered participation in the study. The Johns Hopkins MS Center infusion center currently provides natalizumab infusions for 140 MS patients per month; it is estimated that one-third have a body mass index < 25 kg/m². Participants will be randomized by the study statistician 1:1 to the frequent patient activation arm or standard of care.

Study Procedures/Schedule of Events:

Patients will be consented one month prior to the baseline visit so they can be given adequate notice and can be given a stool sample collection kit to bring it at their next infusion.

At the baseline visit, the following will be done:

- Vital signs and waist circumference
- Patient-Determined Disease Steps
- Health-related quality of life, (Functional Assessment in MS [FAMS]), fatigue (PROMIS fatigue), Pittsburgh Sleep Quality Index (PSQI), self-esteem (Rosenberg Self-Esteem Scale), and physical activity (International Physical Activity Questionnaire) assessments
- Blood for future research collected
- Evaluation of capacity to take and store photos on phone
- Randomization group assigned (participant blinded)
- Stool sample kit collection

At follow-up visits (months 3 and 6), the following will be done:

- Vital signs and waist circumference
- Patient-Determined Disease Steps (month 6 only)

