Age 18-75 years; meets 2010 criteria for MS	To ensure broadly generalizable to the MS patient population
Body mass index (BMI) < 25 kg/m ² , or if higher, participant was unwilling to enroll in calorie restriction study	Only want to enroll overweight or obese individuals if they are unwilling to restrict calories, as calorie timing study unlikely to lead to weight loss
No history of diabetes requiring medication	To avoid unpredictable hypoglycemia
Not pregnant, willing to avoid becoming pregnant during the study, and not breastfeeding	To avoid danger to fetus or threats to milk supply or health
No history of an eating disorder	To prevent relapse of eating disorder
No current use of warfarin	To avoid INR fluctuations
No history of major surgery within past 3 months	To prevent improper wound healing
Have a smart phone with the capability of taking and storing photographs	To provides study team with time stamps indicating timing of oral intake.

4. Drugs/ Substances/ Devices

- a. The rationale for choosing the drug and dose or for choosing the device to be used. N/A
- b. Justification and safety information if FDA approved drugs will be administered for non-FDA approved indications or if doses or routes of administration or participant populations are changed. N/A
- c. Justification and safety information if non-FDA approved drugs without an IND will be administered. N/A

5. Study Statistics

a. Primary outcome variable.

Calorie restriction study: Change in waist circumference

Calorie timing study: Change in metabolism biomarkers

b. Secondary outcome variables.

Calorie restriction study: Change in body mass index, number of pounds lost, percentage adherence to recommended calorie intake, changes in health-related quality of life, changes in fatigue and sleep

Calorie timing study: Adherence to photographing foods, changes in health-related quality of life, fatigue, and sleep

c. Statistical plan including sample size justification and interim data analysis.

Summary statistics (mean \pm standard deviation, median and interquartile range, or number and percentages) will be used to describe the outcomes.

Calorie Restriction:

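### The calorie timing study records no eating window before randomisation and lists no window-adherence outcome, so as planned it cannot identify within-person shortening

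*Combined protocol and SAP*

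**What the plan says.** Secondary Objective B in the Objectives section is "To assess if shortening the time period in which typical calories are consumed during the day improves markers of metabolism", together with fatigue and quality of life. Section 2a (Calorie Timing Study, Overview) sets the size: "We will conduct a pragmatic pilot study in which 40 patients with MS". One arm is assigned "to not changing their current dietary patterns at all", the other "to consuming their total daily calories within a period of 12:00 PM and 8:00 PM".

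The schedule in section 2a states: "Patients will be consented one month prior to the baseline visit". The reasons given for that month are notice and the stool kit. At the baseline visit the only item that bears on eating times is "Evaluation of capacity to take and store photos on phone", and the group is assigned at the same visit. Photos are collected at months 3 and 6, each time covering the period since the previous visit. Section 2c describes twice-weekly prompts to photograph 24 hours of intake and does not limit them to one arm. Section 3 gives the purpose of the photos as timing of intake, and none of its entry criteria concerns usual eating times.

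Section 5a makes change in metabolism biomarkers the primary outcome. The 5b entry begins "Calorie timing study: Adherence to photographing foods" and goes on to quality of life, fatigue and sleep. Section 5c makes the primary analysis intent-to-treat and adds that "secondary analyses will investigate with the actual time of day metrics, as assessed by time stamps of smartphone photos, are predictive of changes in metabolism" (I read the first "with" as a slip for whether). The time-of-day metrics are not defined.

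**The concern.** Shortening is a change from a person's own habit. The plan observes eating times only after allocation, so three things are out of reach.

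- It cannot tell who shortened, or by how much. Someone with a stable short window before and after entry is scored as exposed to a short window, although nothing changed.
- It cannot identify participants who already ate between 12 PM and 8 PM. In the window arm they have nothing to change, and they pull the average effect of assignment down.
- It cannot check, person by person, that the no-change arm kept its pattern. That arm is also being prompted to photograph its food.

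The listed adherence outcome does not fill the gap. Photographing every meal shows that the data are complete, not that the meals fell inside the assigned window. If the biomarkers show no difference, readers will ask first whether the arms ate at different times, and 5b does not commit to reporting that.

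The companion study shows that the counterpart was feasible. The calorie restriction study determines energy requirement before randomisation and lists percentage adherence to the recommended intake as an outcome.

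**Working it through.** The plan gives no alpha, power, effect size or SD for the timing study, so there is no figure of its own to reproduce. Everything below marked as assumed is mine and shows scale only.

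**Inputs from the documents.** 40 patients at 1:1 give 20 per arm. The window from 12:00 PM to 8:00 PM is 8 hours. Prompts go out twice a week. Infusions are every 28 days, so the month between consent and baseline is 4 weeks.

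**1. Level against change.** Take window length as the time-of-day metric. Assume that the window arm eats in exactly 8 hours, that controls do not change, that the usual window has mean 12 hours and SD *s*, and that the metabolic change is *b* times the hours of shortening. Let D = 12 − 8 = 4.

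- Window arm: post-baseline window 8 for everyone; mean shortening D.
- Control arm: post-baseline window equal to the usual one (mean 12, SD *s*); shortening 0.
- Within each arm, one of the two quantities is constant, so their covariance comes only from the arm means and has size D²/4.
- The variance of the post-baseline window is D²/4 + *s*²/2.

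Ratio of the level slope to the true slope, in absolute size: (D²/4) / (D²/4 + *s*²/2), with D²/4 = 4.

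| *s* (hours, assumed) | Ratio |
|---|---|
| 1 | 4 / 4.5 = 0.89 |
| 2 | 4 / 6 = 0.67 |
| 3 | 4 / 8.5 = 0.47 |

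Using change in window as the exposure removes this attenuation under the same assumptions.

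**2. Participants already inside the window.** Let *q* be the share who already eat between 12 PM and 8 PM, and assume no effect in them. The intent-to-treat effect is multiplied by (1 − *q*) and the information by (1 − *q*)². The power column assumes a true standardised effect of 0.8, 20 per arm, two-sided alpha 0.05 and the normal approximation.

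| *q* (assumed) | Effect kept | Information kept | Effective effect | Power |
|---|---|---|---|---|
| 0 | 100% | 100% | 0.80 | 0.716 |
| 10% | 90% | 81% | 0.72 | 0.624 |
| 20% | 80% | 64% | 0.64 | 0.525 |
| 30% | 70% | 49% | 0.56 | 0.425 |

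This shows how much the unmeasured quantity could matter. It is not information that measuring it would recover.

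**3. What the planned photos can show without a baseline.** Comparing mean window length between arms, 20 per arm, t-test at an assumed two-sided alpha of 0.05:

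| Difference (assumed) | Power, SD 2 hours (assumed) | Power, SD 3 hours (assumed) |
|---|---|---|
| 2 hours | 0.869 | 0.538 |
| 3 hours | 0.996 | 0.869 |

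The average separation between the arms is therefore within reach of the planned data.

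**4. Size of a run-in.** 4 weeks × 2 prompts = 8 photo days before allocation, against 26 × 2 = 52 over the 6 months of follow-up.

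**The case against.** A reader might infer that Objective B cannot be tied to any actual shortening, or that a null result could never be explained. The documents do not support either. The comparator is randomised and told not to change, so it estimates the eating window that the other arm would otherwise have had. The prompts are not limited to one arm, so the between-arm difference in photo-derived window estimates average shortening, and step 3 shows that this is feasible at 20 per arm. The data to separate an ineffective schedule from arms that ate alike will exist. What is missing is a defined metric and a commitment to report it by arm.

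A reader might also infer that measuring the baseline window cures the dilution in step 2. It does not. The same people stay in the trial, and a main-effect covariate can reduce residual variance but cannot restore a diluted average. In a pragmatic pilot, the average effect of assignment among all comers is also a legitimate target.

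The attenuation in step 1 is conditional. The exposure analysis is not randomised, and confounding by habit could push it either way. Nor should change in window displace the planned metrics: the Background section gives timing of intake as a rationale of its own.

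Finally, photographing food before baseline may alter habits. Equal reactivity in both arms does not make it harmless, because it could shift both the measured usual window and the baseline samples.

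All of these objections stand. None of them supplies a pre-allocation eating window or a window-adherence outcome.

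**Conclusion.** The point holds in limited form. The plan has no pre-randomisation record of eating times, no entry criterion on them, no outcome for staying within the assigned window, and an exposure analysis that pairs a post-baseline level with a change. As planned, it cannot identify within-person shortening or participants who already ate between 12 PM and 8 PM.

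If the effect depends on shortening, the 5c exposure slope falls to between 0.89 and 0.47 of its true size for an assumed usual-window SD of 1 to 3 hours. That range rests on full adherence, unchanged controls, a usual mean of 12 hours and a proportional effect; the documents give none of these. The (1 − *q*) figures are illustrations under an assumed *q*.

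The intent-to-treat comparison is valid as it stands. This is a worthwhile, low-cost improvement to a secondary objective in a 40-person pilot, not a flaw that invalidates the study.

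**What to change.** 1. **Measure before allocation.** Either ask usual first and last intake times at the baseline visit before the group is assigned, or move the phone check to the consent visit and start the existing twice-weekly prompts then. The questions cost almost nothing. The photos give about 8 days per person with no added visit, at the price of a small burden and possible reactivity before the baseline samples.
2. **Extend the 5c secondary analysis.** Define the time-of-day metrics, and add change in eating window from baseline as an exposure alongside them. The baseline window may also enter as a covariate, or as a prespecified arm-by-baseline-window interaction. State that a main-effect covariate does not reverse dilution of the intent-to-treat effect. An interaction will be imprecise at 20 per arm.
3. **Extend 5b.** List, by arm, eating-window length and the percentage of prompted days with all time-stamped intake between 12:00 and 8:00 PM. Keep photo adherence as a measure of data quality. This needs only wording, because the photos are already collected.

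None of this changes the assigned window, the entry criteria or the primary analysis population.
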